Clinical Trial Protocol

NCT Number: NCT07043829

Protocol ID: PCSAEPF29-2021

Official Title: Effect of Consuming a Cimarrón Bean Extrudate Solution on Platelet Function and Postprandial Biochemical Parameters.

Sponsor: University of Talca, Chile.

Principal Investigator: PhD. [name]

Ethics Approval: Folio 29-2021 (Approved)

Version Date: June 19th, 2025

1. Background

The common bean (*Phaseolus vulgaris*), a legume with high nutritional value, has been shown to have beneficial effects on cardiovascular health. Its bioactive components, including proteins, polyphenols, and fiber, contribute to the modulation of platelet activity. Evidence from previous studies indicates that regular bean consumption may reduce inflammatory markers, oxidative stress, and overall cardiovascular risk, positioning it as a key functional food for the prevention and management of chronic diseases. Incorporating beans into the regular diet could represent a practical strategy to improve cardiovascular health and promote healthy eating habits in the general population. The primary objective of this trial is to obtain preliminary evidence on the acute capacity of the extrudate to reduce thrombotic activity under controlled conditions, minimizing potential confounding factors that could happen when using a delivery vehicle.

2. Objectives

General Objective

To analyze the acute effect of consuming a *Phaseolus vulgaris* L. var. Cimarrón extrudate solution on platelet function, postprandial blood glucose, and total plasma polyphenol levels.

Specific Objectives

1. To evaluate the effect of consuming SPVCE (Solution *Phaseolus vulgaris* L var. Cimarrón extrudate) on platelet function, assessed by PFA and platelet reactivity.
2. To determine the change in postprandial blood glucose after consuming SPVCE.

3. To quantify the effect of consuming SPVCE in postprandial total plasma polyphenol levels.

3. Study Design

Model Description: A single-arm, open-label, acute, non-randomized interventional study in which all participants consumed a single dose of a functional solution containing 10 grams of *Phaseolus vulgaris* L var. Cimarrón extrudate dissolved in water. No placebo or comparator group is included. Outcomes are measured before and after the intervention within the same participants to assess acute changes in platelet function, postprandial glycemia, and total plasma polyphenol levels.

4. Participants

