Table 1. Nutritional analysis carried out on *Phaseolus vulgaris* L. var. “Cimarrón”

Bioactive Compound	
Total Protein (g/100 g DM-Dumas)	29.1
Soluble Protein (mg/mL)	3.8
Amino acids (mg/g Protein)	
Gly.His	55.3
Thr	34.3
Val	36.9
Met	7.4
Ile	31.5
Leu	58.4
Phe	45.3
Lys	54.4
EAA s	323.4
Asp	78.1
Glu	115.0
Ser	48.1

Arg	58.7
Ala	34.4
Pro	34.0
Tyr	24.8
NEAAs	394.3
Macro elements (g/10 g DM)	
P	4.6
K	15.8
Ca	1.1
Mg	1.9
Micro elements (mg/10g DM)	
Mn	14.0
Zn	45.3
Cu	10.3
Fe	105.0
B	18.0
Sugar	
RFO (mmol/100g DM)	5.0
Sucrose (g/ 100g DM)	2.3
Antioxidant capacity	
TPC (mg GA/ 100g DM)	74.5
ORAC (umol TE /100g DM)	9474.9

Table 2. Nutrition facts- *Phaseolus vulgaris* L. var. Cimarrón Extrudate

Nutrition Facts	100 g	Portion (10 g)
Calories (kcal)	227.9	22.79
Total Fat (g)	0.4	0.04
Sodium (mg)	0.62	0.062
Total Carbohydrate (g)	44.29	4.29
Dietary Fiber (g)	17.83	1.78
Total Sugars (g)	6.82	0.68
Includes 0g Added Sugars	0	0
Protein (g)	29.1	2.5

Time line

Participants were scheduled in advance and instructed to arrive after an overnight fast of 10–12 hours. Upon arrival, they completed a digital basic health assessment questionnaire covering medical history, current health status, dietary and nutritional habits, tobacco and alcohol consumption, education level, and socioeconomic status. A phlebotomist inserted an intravenous line to maintain venous access for blood collection, and participants remained at rest throughout the intervention.

1. At time 0 (baseline), blood samples were collected in two tubes containing 3.2% sodium citrate (Ez MedLab Co., Zhejiang, China) for baseline platelet function analysis (platelet reactivity and PFA) and quantification of total plasma polyphenols, and in one serum separator tube (Ez MedLab Co., Zhejiang, China) for baseline glucose measurement.
2. Two hours after SPVCE consumption, an additional serum separator tube was collected for postprandial glucose measurement and quantification of total plasma polyphenols.
3. Six hours after SPVCE consumption, blood samples were again collected in two sodium citrate tubes for postprandial platelet function analysis (platelet reactivity and PFA) and quantification of total plasma polyphenols.

Preparation and administration details

1. **Fasting state:** about 10 to 12 hours of nocturnal fasting; the participant can drink water while in the fasting state.

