2. **Administration of SPVCE:** The participant has 10 to 15 minutes to drink the SPVCE. The research team made the SPVCE, and the self-team supervised the administration.

7. Outcomes

Primary endpoint

- **Platelet function measured by flow cytometry assay:** binding fluorescein isothiocyanate–conjugated anti-fibrinogen antibody (FITC) and PE-conjugated anti-P-selectin (PE) antibody after stimulation with ADP (0.03–30 μ M), collagen-related peptide (CRP; 0.003–3 μ g/mL), and thrombin receptor activator peptide 6 (TRAP-6; 0.05–15 μ M). Measurements performed using a FACSLytic flow

cytometer (BD, San Diego, USA). Analysis performed by Thrombosis Center Research, Talca, Chile.

Secondary endpoints

- 1. Platelet Function (Closure Time):** Measured by PFA-200 (Collagen+ADP cartridge, Siemens Healthcare, Marburg, Germany) at 0 h and 6 h on whole blood. Analysis performed by Thrombosis Center Research, Talca, Chile.
- 2. Baseline and postprandial Glucose:** Serum glucose measured by GOD-POD (glucose oxidase-peroxidase) enzymatic colorimetric method using BS300 Mindray (Shenzhen, China) at time 0h (baseline) and 2 h postprandial. Analysis performed by Clinic laboratory Talca, Chile.
- 3. Plasma total polyphenols concentration:** Prussian blue colorimetric method, measured in plasma at 0 h, 2 h, and 6 h. Analysis performed by Thrombosis Center Research, Talca, Chile.

Safety endpoints: Adverse events, vital signs, and routine clinical laboratory safety tests. Any clinically relevant abnormality will be recorded and reported per the ethics committee's requirements.

Sample handling: specify tubes and processing:

- 1. Flow cytometry platelet reactivity:** Whole blood anticoagulated with 3.2% sodium citrate processed according to Thrombosis Center SOPs, centrifuged at 1200 rpm for 12 minutes at T° ambient, obtaining platelet-rich plasma (PRP). Agonist time-to-stimulation: 10 minutes at ambient temperature and staining 20 minutes at ambient temperature
- 2. PFA-200:** Whole blood anticoagulated with 3.2% sodium citrate processed to Thrombosis Center SOPs in recommended cartridge tube tested within manufacturer's timeframe: 30 minutes after sampling at 15-25 °C.
- 3. Glucose:** Serum separator tubes, centrifuge at 3000 rpm for 8 minutes at ambient temperature, and analyze per Clinic Lab. Talca SOP.

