- 4. Total polyphenols:** Whole blood anticoagulated with 3.2% sodium citrate processed to Thrombosis Center SOPs, centrifuged at 3000 rpm for 8 minutes at ambient temperature, obtaining platelet-poor plasma (PPP), aliquot and store at -80°C until assay if not run immediately.

Laboratories: Thrombosis Center Research, University of Talca (Platelet function assays and total polyphenols), and Clinic Laboratory Talca (glucose).

Visit schedule & sample timing

- 1. Day 0 (Treatment):** Participants arrived in fasting conditions (≥ 8 hours).
- 2. Baseline samples at T0h:** PFA-200, flow cytometry (reactivity), serum glucose, plasma total polyphenols. Administer 10 g extrudate in 500 ml water (supervised).
- 3. Post-dose samples:** T2h-serum glucose, plasma total polyphenols; T6h-PFA-200 Flow cytometry, plasma total polyphenols. Record AEs and vital signs throughout.

Discharge/follow-up: The participant has signed a request for sample storage and subsequent use of the samples in future research. Depending on the option selected (Acceptance or Rejection), the samples will be stored accordingly, labeled with the corresponding code, or discarded following the biological sample disposal protocol of the University of Talca, Chile.

8. Sample size and Statistical considerations

Planned enrollment: 30 participants

Statistical software: GraphPad Prism 10.1.1.

Statistical Plan: Paired analysis comparing pre- and post-dose measures, two-sided $p < 0.05$. More details in the SAP appendix.

9. Criteria for Withholding and Stopping

Withholding Criteria (no intervention on study day):

The investigational product will **not be administered**, and the participant's study visit will be suspended for the remainder of that scheduled 8-hour session if any of the following are present at baseline (pre-dose) or detected during the immediate pre-administration checks:

1. Acute illness or fever on the study day.
2. Fasting blood glucose ≥ 126 mg/dL or ≤ 60 mg/dL at baseline measurement.
3. Blood pressure $\geq 160/100$ mmHg at baseline assessment.

4. Self-reported moderate/severe gastrointestinal symptoms within 24 hours before the visit (e.g., vomiting, severe diarrhea, uncontrolled nausea).
5. Any acute condition deemed by the investigator to increase participant risk or compromise data integrity.

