Normality of data will be evaluated using the Shapiro–Wilk test, and homogeneity of variances will be assessed using Levene’s test where applicable. All statistical tests will be two-sided with the significance level set at $p < 0.05$.

6. Primary Endpoint

- Platelet Function (Flow Cytometry – Dose–Response Analysis): For each activation marker (P-selectin and fibrinogen) and agonist (ADP, TRAP-6, CRP), dose–response curves will be generated using non-linear regression to determine EC₅₀, maximum response, minimum response, and response span per participant. Comparisons of these curve-derived parameters between baseline (0 h) and 6 h post-ingestion will be performed.

The analysis will proceed as follows: For curve-derived parameters (EC₅₀, maximum, minimum, and response span), normality of paired differences between baseline and 6 h will be assessed using the Shapiro–Wilk test. If data are normally distributed, paired t-tests will be used for comparisons; if non-normal, Wilcoxon signed-rank tests will be applied. For the dose–response curves themselves, a two-way ANOVA will be performed to evaluate the effects of treatment (baseline vs. 6 h) and agonist concentration. If assumptions for parametric analysis are met, Sidak’s multiple comparisons post hoc test will be applied. If assumptions are not met and the analysis is non-parametric, a corresponding non-parametric alternative to two-way ANOVA will be used, followed by Dunn’s multiple comparisons post hoc test. Data will be presented as mean \pm SD for normally distributed data and median [IQR] for non-normal data

7. Secondary Endpoints

1. **Platelet Function (Closure Time – PFA-200):** Paired differences between baseline (0 h) and 6 h will be analyzed after testing for normality with the

Shapiro–Wilk test. Normally distributed data will be compared using a paired t-test, and non-normal data using the Wilcoxon signed-rank test.

2. **Baseline and Postprandial Glucose:** Differences between 0 h and 2 h will be analyzed using the same normality testing and paired statistical approach (t-test or Wilcoxon).
3. **Plasma Total Polyphenols Concentration:** Repeated measures at 0 h, 2 h, and 6 h will be analyzed using one-way repeated measures ANOVA if normality assumptions are met, followed by an appropriate post hoc test (e.g., Tukey's or Sidak's) for parametric data. If non-parametric, the Friedman test will be used, followed by Dunn's multiple comparisons post hoc.

8. Missing Data Handling

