- The primary analysis will be conducted as an available-case analysis: only complete pairs of baseline and post-dose measurements will be included for paired comparisons, excluding any missing pairs. The number of pairs included will be reported for each analysis.
- If missing data in the primary variable is $\leq 5\%$, only available-case analysis will be performed without imputation.
- If missing data exceeds 5% or is suspected not to be missing completely at random, sensitivity analyses will be conducted using appropriate methods such as:
 - Linear mixed models for repeated measures (assuming Missing At Random), or
 - Multiple imputation (e.g., predictive mean matching) and comparison with available-case results.
- Participants lacking estimable parameters for a specific variable will be excluded from analyses involving that parameter; actual sample sizes will be reported accordingly.

9. Multiple Comparisons Correction

No formal correction for multiple comparisons will be applied. The primary endpoint analyses are limited to a small set of predefined parameters (EC_{50} , max, min, span) for key activation markers and agonists. Secondary endpoint analyses will be considered exploratory. Given the focused nature of the primary analyses and the sample size, results will be interpreted with caution regarding multiplicity. Where applicable, post hoc tests controlling type I error (e.g., Sidak's or Dunn's tests) will be used following ANOVA or non-parametric analyses.

10. Safety and Adverse Events

Gastrointestinal symptoms and any adverse events will be summarized as frequencies and percentages. Where applicable, events will be reported by post-ingestion time point.

11. Sample Size and Power

The planned sample size of **n = 30** is based on feasibility and prior experience in acute postprandial studies. With n = 30 for paired comparisons, the study has approximately **80% power** to detect a medium effect size (Cohen's $d \approx 0.5$) at $\alpha = 0.05$ (paired t-test).

12. Presentation of Results

Results will be presented in tables and figures. Tables will include descriptive statistics per time point, changes from baseline with 95% confidence intervals, and adjusted p-values where applicable. Figures will present time–response profiles, dose–response curves, and bar plots of key comparisons.

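### Polyphenol plasma may be assayed fresh or frozen, and no visible rule keeps a participant's 0, 2 and 6 h samples in one storage state and one run, so a time-aligned assay shift could pass for a product effect

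*Combined protocol and SAP*

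**What the plan says.** Protocol section 7, secondary endpoint 3, defines the outcome as "Prussian blue colorimetric method, measured in plasma at 0 h, 2 h, and 6 h". Sample handling item 4 in the same section covers these samples: "Whole blood anticoagulated with 3.2% sodium citrate processed to Thrombosis Center SOPs, centrifuged at 3000 rpm for 8 minutes at ambient temperature". It then adds the instruction to "aliquot and store at -80°C until assay if not run immediately". That sentence is the only storage rule for this assay.

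Protocol section 3 describes the design: "No placebo or comparator group is included", and "Outcomes are measured before and after the intervention within the same participants". SAP section 7, item 3, gives the analysis: "Repeated measures at 0 h, 2 h, and 6 h will be analyzed using one-way repeated measures ANOVA", with Friedman's test as the non-parametric alternative. Neither has a term for run or storage state. SAP section 9 sets the endpoint's standing: "Secondary endpoint analyses will be considered exploratory".

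One further passage bears on the same endpoint. In the Protocol's time line (under section 5), item 2 says that at two hours "an additional serum separator tube was collected for postprandial glucose measurement and quantification of total plasma polyphenols". Items 1 and 3 there use citrate tubes at 0 h and 6 h.

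**The concern.** A participant's three samples are drawn over six hours. If each is assayed as it arrives, they will probably fall in different runs. If some are assayed fresh and others frozen, one participant can contribute a frozen 0 h value and a fresh 6 h value. The visible text allows both. It does not ask for random order within a run, for an analyst unaware of time point, or for a record of run and storage state.

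A controlled trial would absorb much of this, because an assay shift tied to time would affect both arms. Here the within-participant change is the whole of the evidence for specific objective 3. If storage state or run shifts the reading in the same direction at the same time point across participants, the analysis has nothing with which to tell that shift from a product effect, and it cannot be fully removed afterwards.

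**Working it through.** **Inputs.** n = 30 (Protocol section 8; SAP section 4). Two-sided 5% level (SAP section 5). Assay offsets are assumptions, expressed in SDs of the paired difference (σ_d), because the documents give no assay precision. No true change is assumed throughout.

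**The plan's own figure.** SAP section 11 states about 80% power at d ≈ 0.5. The normal approximation gives Φ(0.5 × √30 − 1.96) = Φ(0.779) = 78.2%. The exact noncentral t gives 75.4%. This point does not depend on that figure, but the formula is the same: a spurious shift of 0.5 σ_d is detected exactly as often as a true one.

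**1. Shift fully aligned with time point, all participants.** The rejection probability is that of a noncentral t with 29 degrees of freedom, noncentrality δ√30 and critical value ±2.045.

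| Shift δ (σ_d) | δ√30 | Paired t-test rejects |
|---|---|---|
| 0 | 0 | 5.0% |
| 0.1 | 0.55 | 8.3% |
| 0.2 | 1.10 | 18.5% |
| 0.3 | 1.64 | 35.5% |
| 0.5 | 2.74 | 75.4% |

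The planned omnibus test behaves alike. Put the 0 h sample out of line with 2 h and 6 h, and assume compound symmetry, so that σ_d = √2 × the within-participant SD. Then λ = 30 × (2/3) × 2δ² = 40δ², with 2 and 58 degrees of freedom. For δ = 0.2, 0.3 and 0.5, λ = 1.6, 3.6 and 10, and the test rejects 18.0%, 36.1% and 79.4% of the time.

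**2. Aligned shift in only some participants.** A 0.5 σ_d shift in a share f moves the mean by 0.5f. For f = 0.25 the mean shift is 0.125 and rejection is about 10%. For f = 0.5 it is 0.25 and rejection is about 26%. This ignores the small extra variance from mixing shifted and unshifted participants.

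**3. Random run offsets, independent between participants.** The difference is e_i + b_i, with b_i of mean zero. The mean difference stays at zero and the test's own SD takes in the extra variance, so rejection stays at 5%. The cost is precision: with b_i of SD 0.5 σ_d, the variance rises from 1 to 1.25 and the confidence interval widens by √1.25 = 1.12, or 12%.

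**4. Random run offsets shared by k participants.** The differences are now correlated, with intraclass correlation 0.25/1.25 = 0.2, and the t-test ignores this. The design effect is 1 + (k − 1) × 0.2.
- k = 3: design effect 1.4; 1.96/√1.4 = 1.66; two-sided tail about 10%.
- k = 5: design effect 1.8; 1.96/√1.8 = 1.46; two-sided tail about 14%. Simulation of the t-test gives about 15%.

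The documents do not say how many participants were seen per day or shared a run.

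**5. After the change.** If a participant's three samples share an offset b, the change is (y₆ + b) − (y₀ + b) = y₆ − y₀. The offset cancels and the rate returns to 5%. Sample size and power figures do not change.

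**The case against.** The strongest reply is that separate runs do not in themselves produce false positives. That is right, and step 3 shows it: independent offsets only add noise. A reader might infer that assaying every sample immediately must line run differences up with time. It need not. Bias requires a consistent direction across participants, or runs shared by several of them.

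Second, the large percentages in step 1 belong to the worst case. They need the same-direction shift in every participant, for instance nearly all 0 h samples frozen and nearly all 6 h samples fresh. No text describes that pattern, and step 2 shows how quickly the figure falls when fewer participants are affected.

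Third, batching and run layout are ordinary content for a laboratory SOP, and the Thrombosis Center SOPs are not available here. A reader might infer that samples go into whatever run is convenient; the documents do not say so, and they leave the word immediately undefined. What remains is that the protocol's own sentence permits both storage states.

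Fourth, a reader might argue from the polyphenol content in Table 1 that the true signal must be small, so that any assay shift would swamp it. The documents give neither absorption nor assay precision, so that step is unsupported and nothing here relies on it.

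Finally, the endpoint is secondary and exploratory in a trial that seeks preliminary evidence. That limits the priority. It does not remove the point, since this endpoint alone answers one of the three specific objectives.

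**Conclusion.** The point holds as a gap in the handling rule. The visible text permits mixed storage states and separate runs within a participant, and neither the design nor the analysis could separate a time-aligned shift from a product effect. It does not show that such a shift occurred.

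The size depends wholly on an unknown offset. Under the assumed offsets, the false-positive rate runs from the nominal 5% (independent offsets), through about 10% to 15% (a random 0.5 SD offset shared by three or five participants) and about 10% to 26% (a 0.5 SD shift in a quarter or half of participants), to 75.4% (a 0.5 SD shift aligned in all). Priority is moderate.

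The 2 h tube is a firmer problem in the same endpoint. The time line names a serum separator tube, while Sample handling item 4 specifies citrate plasma. If the time line is literal, the matrix itself differs by time point, and assaying the samples in one run would not correct that.

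**What to change.** Replace the storage rule in Protocol section 7, Sample handling, item 4, with wording such as: *All polyphenol aliquots (0, 2 and 6 h) are frozen at -80°C. Each participant's three aliquots are thawed once and assayed together in the same run, in random order. Run and storage time are recorded for every aliquot.*

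Recruitment and blood collection are described in the past tense, so some assays may already be done. In that case, report storage state and run for each sample, and add to SAP section 7, item 3, a sensitivity analysis restricted to participants whose three samples shared storage state and run. If few or none qualify, say so, and state that an assay shift cannot be excluded as an explanation for a change.

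Reconcile the 2 h tube type between the time line and Sample handling item 4, and report which matrix was used at each time point.

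The cost is small. Storage at -80°C is already provided for, and visits, blood volume and sample size are unchanged. The one loss is a same-day polyphenol result, which no decision in the documents uses.

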Action: If withholding criteria are met, the product will **not** be given during that 8-hour session. The study physician documents the reason, provides appropriate care/advice, and notifies the principal investigator. Rescheduling of the visit may occur only according to the trial's rescheduling policy (if allowed by the protocol); otherwise, the visit is recorded as not completed.

Stopping Criteria (Immediate cessation during session):

The study intervention will be **stopped immediately** for an individual participant during the 8-hour session if any of the following occur:

1. Any **serious adverse event (SAE)** possibly, probably, or related to the product (e.g., anaphylaxis, respiratory distress, hospitalization).
2. Acute clinically significant change in monitored clinical parameters judged to be related to the product (for example: new onset chest pain, severe hypotension or hypertension not responsive to initial measures, severe arrhythmia).
3. New laboratory or point-of-care result during the visit indicating acute organ injury (e.g., markedly abnormal glucose) that the investigator deems unsafe to continue.
4. Severe or worsening gastrointestinal reaction during the session (e.g., persistent vomiting, dehydration) that requires medical intervention.
5. Participant requests to stop or withdraw consent at any time.

Action: On stopping, immediate medical evaluation is provided, the event is documented in the case report form, the principal investigator is notified, and appropriate medical referral (including emergency care) is arranged if needed. The participant's further participation in subsequent visits will be decided according to the protocol and safety assessment.

Additional operational details

1. Who decides: the study physician and/or principal investigator make withholding/stopping decisions. Site staff follow their instructions.

2. Monitoring during the 8-hour visit: vital signs and symptom checks per protocol schedule; any trigger must be recorded with time and action taken.
3. Reporting: all SAEs and stopping events are reported per the trial safety reporting plan and institutional requirements.
4. Re-enrollment/rescheduling: any decision to allow the participant to return for another 8-hour session must follow the protocol's eligibility and rescheduling rules and occur only after medical clearance.

10. Data management and Ethics

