Records will be kept confidential by the responsible researcher. Participant names or identifiers will not be used. Blood samples will be labeled with codes and will not be linked to personal data. Identity and health information will not be disclosed and will remain confidential. Study approved by the University of Talca Scientific Ethic Committee (Folio 29-2021).

Statistical Analysis Plan (SAP)

NCT Number: NCT07043829

Protocol ID: PCSAEPF29-2021

Official Title: Effect of Consuming a Cimarrón Bean Extrudate Solution on Platelet Function and Postprandial Biochemical Parameters.

Sponsor: University of Talca, Chile.

Principal Investigator: PhD. [name]

Ethics Approval: Folio 29-2021 (Approved)

Version Date: June 19th, 2025

1. Introduction: This Statistical Analysis Plan (SAP) outlines the methods and procedures for analyzing the data from the clinical trial investigating the acute effects of a Cimarrón Bean Extrudate solution on platelet function and postprandial biochemical parameters.

2. Analysis Populations

- **Per-protocol (pp) population:** Includes all participants who complete the 8-hour observation period and have valid measurements for the outcomes of interest without major protocol deviations (e.g., incomplete fasting, incomplete product ingestion, prohibited medication use). Sensitivity analyses will be conducted in the PP population to verify robustness.
- **Available Case Analysis:** An analysis based on all available data pairs for each outcome; participants with missing paired data will be excluded from that specific analysis.

3. Software: All statistical analyses will be performed using *GraphPad Prism version 10*.

4. General Analysis Design

- The planned sample size is **n = 30**.
- Measurements were obtained at baseline (0 h, pre-ingestion) and at **2 h** and **6 h** after consumption of the extrudate solution.

- Continuous variables will be expressed as mean \pm standard deviation (SD) when approximately normally distributed, or median [interquartile range, IQR] when non-normal.
- Categorical variables will be presented as frequency and percentage. For each time point, the mean/median and change from baseline will be reported.

5. Assessment of Normality and Homogeneity

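### The planned polyphenol tests in SAP 7.3 use only participants with all three samples, so they discard valid baseline pairs that the SAP's available-case rule would keep

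*Combined protocol and SAP*

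**What the plan says.** Protocol section 7 lists plasma total polyphenols as the third secondary endpoint: "Prussian blue colorimetric method, measured in plasma at 0 h, 2 h, and 6 h". It is the only secondary endpoint with three time points; closure time and glucose have two each.

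SAP 7, item 3, sets the test: "Repeated measures at 0 h, 2 h, and 6 h will be analyzed using one-way repeated measures ANOVA if normality assumptions are met", followed by Tukey's or Sidak's comparisons. The non-parametric branch is Friedman followed by Dunn's test.

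Two other sections say who is included. SAP 2 defines the available-case analysis: "An analysis based on all available data pairs for each outcome; participants with missing paired data will be excluded from that specific analysis". SAP 8 makes available-case the primary analysis and adds that "only complete pairs of baseline and post-dose measurements will be included for paired comparisons, excluding any missing pairs".

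SAP 8 also names a linear mixed model or multiple imputation, as sensitivity analyses to be run if missingness exceeds 5% or is suspected not to be completely at random. No section says what happens to a participant with two of the three polyphenol values.

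**The concern.** The available-case rule is written in pairs, and the polyphenol test works in triples. For closure time and glucose the two coincide. For polyphenols they separate as soon as one sample is lost:

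- A participant without the 2 h value still has a valid 0–6 h pair.
- A participant without the 6 h value still has a valid 0–2 h pair.
- Under repeated-measures ANOVA or Friedman in standard form, both participants leave the omnibus test and the comparisons that follow it.

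Specific Objective 3 asks how postprandial polyphenols change, and the 0–2 h and 0–6 h contrasts answer it. As written, the number behind each contrast depends on a choice the SAP leaves open, and that choice could be made after the data are seen. The tested contrasts could also rest on fewer participants than the changes from baseline that SAP 4 and SAP 12 promise to tabulate.

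**Working it through.** **Inputs from the documents.** SAP 4: "The planned sample size is n = 30". SAP 5: "All statistical tests will be two-sided with the significance level set at $p < 0.05". SAP 11: "approximately 80% power to detect a medium effect size (Cohen's $d \approx 0.5$) at $\alpha = 0.05$ (paired t-test".

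**The plan's own power figure.** The normal approximation gives Φ(0.5·√30 − 1.96) = Φ(0.779) = 78.2%, within two points of the stated 80%. The exact two-sided paired t-test (noncentral t, 29 df, noncentrality 0.5·√30 = 2.74) gives 75.4%. I use the exact t below because it is the test SAP 11 names. The difference does not bear on this point.

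**Do the named tests need complete triples?** I ran them on simulated data, 30 participants by 3 times.

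- With no missing value, repeated-measures ANOVA has error df (30 − 1)(3 − 1) = 58.
- With one 2 h value removed, the ANOVA routine stopped because the data were unbalanced. After that participant was dropped, the error df was (29 − 1)(3 − 1) = 56.
- Friedman returned no result while the value was missing.
- A mixed model on the same data used 89 observations from all 30 participants.

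This shows the tests in standard form. The documents do not say how the software named in SAP 3 treats an incomplete row, so nothing here relies on that.

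**How many pairs are lost?** The documents give no rate, so the loss q per sample is an assumption, taken as independent between samples.

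Case A, any of the three samples can be lost: triples = 30(1 − q)³, pairs per baseline contrast = 30(1 − q)², difference = 30q(1 − q)².

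Case B, baseline always present: triples = 30(1 − q)², pairs = 30(1 − q), difference = 30q(1 − q).

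| q | A: triples | A: pairs | A: lost | B: triples | B: pairs | B: lost |
|---|---|---|---|---|---|---|
| 1% | 29.1 | 29.4 | 0.3 | 29.4 | 29.7 | 0.3 |
| 2% | 28.2 | 28.8 | 0.6 | 28.8 | 29.4 | 0.6 |
| 5% | 25.7 | 27.1 | 1.4 | 27.1 | 28.5 | 1.4 |
| 10% | 21.9 | 24.3 | 2.4 | 24.3 | 27.0 | 2.7 |

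In case A, the chance that at least one of 30 participants loses a valid baseline pair is 1 − [1 − 2q(1 − q)²]³⁰: 45% at q = 1%, 69% at 2%, 94% at 5% and 99.5% at 10%. So the question is likely to arise, though at low rates for very few people.

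**What does that cost in power?** Exact paired t, d = 0.5, two-sided 0.05, counts rounded to whole participants:

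- A, 5%: 27 pairs (70.6%) against 26 (68.8%), 1.8 points.
- A, 10%: 24 pairs (65.0%) against 22 (60.9%), 4.1 points.
- B, 5%: 28 or 29 pairs (72.3% or 73.9%) against 27 (70.6%), 1.7 or 3.3 points.
- B, 10%: 27 pairs (70.58%) against 24 (65.04%), 5.5 points.

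The range is about 2 to 6 points. The value d = 0.5 is the SAP's generic paired-test effect size, not a polyphenol assumption, and these are unadjusted contrasts.

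**The case against.** Several stronger readings are tempting, and the documents do not support them.

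**That the SAP states two conflicting rules.** It never says complete triples only; that follows from the tests it names. The SAP 8 pair rule is confined to paired comparisons, and the exclusion clause in SAP 2 can be read as allowing an incomplete participant to be dropped from the ANOVA. What stands is an unstated rule for three-time data, and named tests that do not deliver the pair-based inclusion of SAP 2.

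**That the SAP 8 fallback cannot apply to polyphenols.** The limit to the primary variable appears only in the bullet on missingness up to 5%. The next bullet, which triggers the mixed model or imputation, carries no such limit. It may cover polyphenols, and losses linked to intolerance would plausibly meet its second condition. Even so, the mixed model is one of two examples, conditional, and a sensitivity analysis only.

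**That the 0–2 h estimate is selected on tolerating the product.** A reader might infer this from the Protocol section 9 stopping rule, which applies "for an individual participant during the 8-hour session if any of the following occur". But that rule stops the study intervention, a single drink, and does not say the 6 h draw is cancelled. A missing 6 h value after stopping is an inference, although withdrawal of consent could cause one. In addition, SAP 4 and SAP 12 report changes from baseline without tying them to the ANOVA set. The restriction concerns the test and its post hoc comparisons, not necessarily every reported estimate.

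**That the stakes are low.** This is fair. SAP 9 calls secondary analyses exploratory, there is one supervised session with a venous line in place, and the loss rates are assumed.

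**Conclusion.** The point holds as a cheap improvement to an exploratory analysis. Followed in standard form, SAP 7.3 removes valid 0–2 h or 0–6 h pairs from the polyphenol test whenever one post-dose sample is missing, while SAP 2 defines the available-case set by pairs. At an assumed independent loss of 5% to 10% per sample, the cost is about 1.4 to 2.7 pairs per contrast, or about 2 to 6 points of power at d = 0.5. At 1% to 2% it is 0.3 to 0.6 of a pair, and with no missing samples it is nothing. I claim no bias of a given size, because the documents do not establish who would be missing or why. The primary endpoint is not affected.

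**What to change.** In SAP 7, item 3:

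1. Make the main parametric analysis a linear mixed model with time as a three-level factor and participant as random effect, fitted to all available samples. Report the 0–2 h and 0–6 h contrasts with 95% confidence intervals and the number of participants contributing to each.
2. If the non-parametric branch is used, keep Friedman and Dunn's on complete triples, say so, and add Wilcoxon signed-rank results on the available 0–2 h and 0–6 h pairs, each with its n.
3. In SAP 8, state whether the sensitivity-analysis trigger applies to secondary outcomes.

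The cost is SAP wording only: no new samples or participants. SAP 8 already names the model. The downside is that it assumes missing at random. With no missing samples it gives the same result as the planned ANOVA when the within-participant correlation is not negative; on the complete simulated data above both gave F = 3.605.
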